### 4.4 Pharmacokinetic (PK) population

Pharmacokinetic (PK) population includes all randomized subjects who receive at least 1 dose of MT-7117 and who have at least 1 post-dose value for plasma concentration without important protocol deviations which may affect the PK of MT-7117.

## 5. GENERAL CONSIDERATIONS

### 5.1 Number of digits to report (present in TFL)

**Table 3 Number of decimal places (DP) or significant digits (SD)**

Statistic	Specification	Apply to
Minimum, maximum	same number of DPs as the data provided in the datasets	All original, i.e. non-derived, data provided in the datasets
mean, median, confidence intervals	one more DP than the raw data	All
SD	one more DP than the raw data	All
Percentages	1 DP	All
p-values	3 DP	All
Odds Ratio	2DP	All
Rate	2DP	All

### 5.2 Significance level and confidence interval

The statistical tests will be performed as two-sided with significance level of 5%.

The two-sided confidence intervals will be determined with a confidence level of 95%.

### 5.3 Descriptive statistics values to calculate

Where appropriate, variables will be summarized descriptively (frequency and percent will be summarized for categorical variables; mean, standard deviation [SD], median, minimum, and maximum will be presented for continuous variables) by analysis visit and by treatment group.

The denominator for the percentages will be the total number of subjects in the treatment group and Analysis Set being presented, unless otherwise specified (e.g. on some occasions,

percentages may be calculated out of the total number of subjects with available data at a particular visit and/or time point).

Summary statistics required for PK or related data are described in relevant sections later.

## 5.4 Derived variables and data convention

### 5.4.1 Derived variables for diary data

For this study, only the sunlight exposure between 1 hour post sunrise and 1 hour pre-sunset is considered and collected. The following wording is not repeated.

The subjects will record in their diaries for the sunlight exposure periods (start/end time), prodromal symptom periods, and pain periods. The subjects' sunlight exposure start and end times will be compared with their state capital cities sunrise and sunset times. The sunlight exposure time beyond the interval (from 1 hour post sunrise to 1 hour pre-sunset) will be excluded from the analyses unless it is specified in a different way.

The analysis windows are defined in the table below. The nominal day for each week relative to the first dose day will be used. Day1 is the first dose day.

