5.3.2.6 Visit 7 (Week 12, Day 85±7)

The following assessments will be performed (please refer to Table 5.1-1 for details regarding the complete time and events schedule for this study):

- Abbreviated physical examination (including body weight).
- Vital signs (including sitting blood pressure, pulse rate, and oral body temperature).
- Routine laboratory evaluations (hematology; biochemistry; coagulation; urinalysis).
- Urine pregnancy test (for female subjects of child-bearing potential only).
- Blood sampling for PK analysis.
- Dispensing of MT-7117 or placebo.
- Medication accountability.
- Review sunlight exposure diary (re-educate subject if necessary).
- AE and concomitant medication recording.

5.3.2.7 Visit 8: End of Treatment Visit (Week 16, Day 113±7 or Early Termination)

Subjects will attend the end of treatment visit at Week 16 or early termination. The following assessments will be performed (please refer to Table 5.1-1 for details regarding the complete time and events schedule for this study):

- Abbreviated physical examination (including body weight).
- 12-lead ECG.
- Vital signs (including sitting blood pressure, pulse rate, and oral body temperature).
- Routine laboratory evaluations (hematology; biochemistry; coagulation; urinalysis).
- Plasma porphyrin and erythrocyte protoporphyrin sample collection.
- Urine pregnancy test (for female subjects of child-bearing potential only).

- Blood sampling for PK analysis (at the visit and 3 to 4 hours after the first PK sample collection [both post-dose]).
- Medication accountability.
- Subject Questionnaire for study medication.
- PROMIS-57 questionnaire.
- PGIC.
- Review sunlight exposure diary (re-educate subject if necessary).
- Melanin density evaluation as measured by spectrophotometer.
- Nevi evaluation and biopsy (for any nevi of clinical concern to the dermatologist or other qualified site staff).
- Optional skin biopsy for exploratory pharmacodynamics analysis.
- In-clinic sunlight exposure test: Perform a formalized collection of the subject's time to onset of 1st prodromal symptom in sun-exposed setting (e.g. preferably outside or by window) using timer.
- AE and concomitant medication recording.
- Fitzpatrick skin type assessment.

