6.7 Efficacy Assessments

6.7.1 Primary Efficacy Endpoint

6.7.1.1 Sunlight Exposure Diary

The sunlight exposure diary will be completed on a daily basis from Screening to the follow-up visit by the subjects. An example of the sunlight exposure diary (extract) is presented in Section 14.3 (Appendix 3).

Subjects will record their sunlight exposure time in the sunlight exposure diary. For each sunlight exposure, they will record the presence, duration (onset time of the first symptom and recovery time) and severity of the prodromal symptoms. Pain, its severity and duration (onset time and recovery time) will also be recorded separately in the dedicated part of the diary. The severity of prodromal symptoms and pain will be measured using an 11-point Likert scale ranging from 0 to 10, with 0 indicating no symptom and 10 indicating greatest severity of symptom.

Subjects will be instructed to recognize the following photo-provoked symptoms as prodromal:

- Burning/hotness/heating up
- Tingling
- Itching/scratchy
- Stinging
- Others

Subject responses in the sunlight exposure diary will be used to investigate the primary

efficacy endpoint. The data from the diary will also be used for the secondary and other efficacy assessments.

Further details will be provided in a separate study reference manual, and statistical assessment methods for this study endpoint are described in Section 10.2.2.1.

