7.1.2 Study Drug Supply

The Sponsor will provide MT-7117 and placebo [REDACTED] in [REDACTED] to each site, for each subject, for the duration of their participation in the study. The Investigator, a study nurse, or the hospital pharmacy will dispense a sufficient quantity of MT-7117 [REDACTED] [REDACTED] consistent with each subject's daily dosage requirement and study visits according to the protocol. Specifically, MT-7117 or matching placebo [REDACTED] (each [REDACTED] [REDACTED] of MT-7117 and matching placebo) will be dispensed in a manner consistent with each subject's daily dosage requirement (for blinded treatment equaling or mimicking MT-7117 at [REDACTED] or [REDACTED] day active medication or placebo, subjects will receive a total of 6 blinded [REDACTED] per day).

Subjects will be instructed to bring their study medication with them to each visit and the Investigator or designee will ensure the subject has a sufficient supply of medication according to their blinded, randomized treatment group to last until the next scheduled visit. Subjects will return all study medication that may remain in their possession to the study staff at the end of treatment visit. In cases where subject forget to return to the clinic with their [REDACTED], sites will be instructed to inquire as to the subjects daily dosing compliance, capturing total number of days missed. Subjects will be instructed to return medication packaging at the follow up visit.

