## 2. STUDY ENDPOINTS

### 2.1 Primary Efficacy Endpoints

- Change from baseline in average daily time (minutes) to first prodromal symptom associated with sunlight exposure between 1 hour post sunrise and 1 hour pre-sunset at Week 16 (Visit 8).

To calculate the average daily sunlight exposure time to first prodromal symptom, a 14-day window on or before a visit (Week 2, 4, 6, 8, 10, 12, 14, and 16) will be used. For baseline, a 14-day window before Day one will be used. A 14-day window will be applied to similar situations for other efficacy endpoints.

The subjects' diary data will be used to derive this and other endpoints based on sunlight exposure time. The details will be given in section 5.4.1. Minute will be used as unit for duration for this and other endpoints.

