**Table 4 Analysis Visit Window for diary data**

Analysis Visit	Nominal day	Window
Baseline	-1	Day -14 to -1
Week 2	14	Day 1 to 14
Week 4	28	Day 15 to 28
Week 6	42	Day 29 to 42
Week 8	56	Day 43 to 56
Week 10	70	Day 57 to 70
Week 12	84	Day 71 to 84
Week 14	98	Day 85 to 98
Week 16	112	Day 99 to 112
Week 22 (FU)		the latest 1 to 14 days before FU not overlapping with the Double-Blind Period.

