#### **5.4.10 Study Treatment Exposure**

The duration of exposure is calculated as the total number of days that the subject has been treated with double-blind study medication— that is, from the treatment start date to the date of their EOT visit. For subjects lost to follow up, the treatment end date is taken to be the date of their last visit. Interruptions, compliance, and dose changes are not taken into account for duration of exposure.

Duration of exposure (days) = EOT visit date – first treatment distribution date +1.

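### The fixed Week 16 diary window (Days 99–112) has no cut-off at Visit 8, so completers seen on Days 106–111 have 6 to 1 post-treatment days in the primary value

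*SAP*

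**What the plan says.** The primary endpoint is the change from baseline at Week 16, tied by name to Visit 8 in Protocol 2.2.1 and SAP 2.1. For the averaging period SAP 2.1 says "a 14-day window on or before a visit (Week 2, 4, 6, 8, 10, 12, 14, and 16) will be used", and Protocol 10.2 is to the same effect.

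SAP 5.4.1 puts this into practice with fixed days: "The nominal day for each week relative to the first dose day will be used". Table 4 then gives Week 16 as Days 99–112. Only the Week 22 row refers to the treatment period; it takes "the latest 1 to 14 days before FU not overlapping with the Double-Blind Period". The Week 2 to Week 16 rows have no such condition.

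Treatment ends at Visit 8, which Protocol 5.3.2.7 heads "Visit 8: End of Treatment Visit (Week 16, Day 113±7 or Early Termination". Protocol 7.1.2 adds: "Subjects will return all study medication that may remain in their possession to the study staff at the end of treatment visit". The diary does not stop there: "The sunlight exposure diary will be completed on a daily basis from Screening to the follow-up visit by the subjects" (Protocol 6.7.1.1). One qualified diary day is enough for a window value (SAP 5.4.1.1), and the primary mixed model takes all available data (SAP 7.11.1). SAP section 8 declares no changes from the protocol.

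**The concern.** For a subject who completes treatment and attends Visit 8 a few days early but within the permitted range, the days between Visit 8 and Day 112 belong to follow-up. They are not on or before the visit, yet Table 4 counts them as Week 16. If the effect fades after the last dose, such days pull the active arms' Week 16 means towards untreated values, and the contrast with placebo shrinks. The cause is appointment scheduling and has nothing to do with how the subject responded.

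The same windows feed the secondary exposure-duration endpoints (SAP 5.4.1.2 and 5.4.1.3). The rank-based analysis with multiple imputation does not help, because it fills only missing values and takes post-treatment values as observed.

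**Working it through.** **Inputs**
- Week 16 window: Days 99–112, with Day 1 the first dose (SAP Table 4).
- Visit 8: Day 113±7 (Protocol 5.3.2.7).
- Last treatment day: taken as the day of Visit 8. This is an inference. Protocol 5.3.2.7 lists "Blood sampling for PK analysis (at the visit and 3 to 4 hours after the first PK sample collection [both post-dose", so a dose precedes both samples, and SAP 5.4.10 counts exposure "from the treatment start date to the date of their EOT visit".
- Follow-up visit: 6 weeks (42 days) after Visit 8 or early termination (Protocol 5.3.3), with ±10 days in the schedule.

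**The plan's own figures**
- Week 16 window: 16 × 7 = 112 and 112 − 13 = 99, as in Table 4.
- Visit 8: 16 × 7 + 1 = 113, so the range is 106 to 120.
- Visit 9: 113 + 42 = 155. All agree with the documents.

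**Completers.** Post-treatment days in the window = max(0, 112 − v), where v is the day of Visit 8.

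| Visit 8 day | 106 | 107 | 108 | 109 | 110 | 111 | 112–120 |
|---|---|---|---|---|---|---|---|
| Post-treatment days of 14 | 6 | 5 | 4 | 3 | 2 | 1 | 0 |

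- Maximum: 6/14 = 43%. Six of the 15 permitted visit days are affected.
- If visits were uniform over Days 106–120 (assumption): (6+5+4+3+2+1)/15 = 21/15 = 1.4 days, and 1.4/14 = 10%.
- If the last dose were instead taken the day before Visit 8, each count up to v = 112 rises by one and the uniform mean is 28/15 = 1.9 days.

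These are calendar days. SAP 5.4.1.1 averages only days with non-zero exposure, so a given subject's share can be higher or lower.

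**Possible dilution (illustration).** Suppose post-treatment days keep a fraction r of the effect and qualified days are evenly spread. A Day 106 completer shows (8 + 6r)/14 of it: 57% at r = 0, 79% at r = 0.5, 100% at r = 1. The uniform-visit average is (14 − 1.4 + 1.4r)/14: 90%, 95% and 100%.

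**A fully visit-anchored window, for comparison**
- Visit 8 on Day 106 gives Days 93–106. It shares 8 days with Table 4 and takes 6 (Days 93–98) from the Week 14 window (Days 85–98).
- Visit 8 on Day 120 gives Days 107–120. It shares 6 days with Table 4 and leaves Days 99–106 in no window.

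**Early terminators.** With termination on Day e, taken as the last day on drug, and follow-up on Day e + 42, the post-termination days in Week 16 run from max(99, e + 1) to min(112, e + 42).
- All 14 days are post-termination when e is at least 112 − 42 = 70 and at most 98. The lower limit is Day 60 with follow-up at 52 days and Day 80 at 32 days.
- For e = 70, Days 71–112 fill the Week 12, 14 and 16 windows completely.
- The Week 22 window for e = 70 would be Days 98–111, of which 13 are also Week 16 days. For e = 84 it would be Days 112–125 (1 shared day), and for e = 98 Days 126–139 (none). This overlap arises only if the Double-Blind Period ends at the actual Visit 8.

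**The case against.** Fixed windows are a reasonable way to implement the protocol. Its wording allows for time points as well as visits; Weeks 6, 10 and 14 have no visit, and Week 2 is only a laboratory collection. SAP 2.1 defers the details to 5.4.1. A reader might infer that the SAP silently replaced the protocol's definition, but the documents do not support that for the schedule as a whole. What stands is narrower: Week 16 is tied to Visit 8, and days after Visit 8 cannot be on or before it.

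A reader might also infer that early leavers' off-drug days are scored in error. The documents do not support that either. Protocol 4.5 encourages subjects who stop treatment to complete all visits and procedures, the efficacy set is analysed by randomized arm, and all available data are used. This fits a treatment-policy reading, although neither document states one. Deleting those days would replace it with reliance on missing at random.

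Nor can one say that an on-treatment versus off-treatment comparison is spoiled, because none is planned. The primary mixed model and the rank-based analysis stop at Week 16, and the only specific use found for the Week 22 diary value is the pooled scatter plot against melanin density in SAP 7.11.3.

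Some protection exists. The per-protocol set requires completion of Week 16, so it should drop early terminators, but it keeps completers with an early Visit 8. The blinded data review (SAP 7.1) may add handling rules, but it is not bound to add this one.

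Finally, any loss of effect within 1 to 6 days is unproven. The Day 14 half-lives of 10.56 to 18.97 hours (Protocol 1.5) put five half-lives at 2.2 to 4.0 days, yet Protocol 3.2 allows 6 weeks to evaluate pigmentation recovery.

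**Conclusion.** The point holds for completers. Table 4 lets 6 to 1 post-treatment days, at most 43% of the calendar window, into the primary Week 16 value when Visit 8 falls on Days 106–111. It lets in none when Visit 8 falls on Day 112 or later, which includes the nominal day. This rests on the last dose being taken on the day of Visit 8.

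The direction, if the effect fades, is towards no difference from placebo. The size is unknown. The mean of 1.4 days, and any statement that 6/15 = 40% of completers are affected, depend on a uniform visit spread that the documents do not give.

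For early terminators the defect is a missing statement of how post-termination days are treated. The double use of days in Week 16 and Week 22 depends on an undefined term, the end of the Double-Blind Period. The matter should be settled before unblinding.

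**What to change.** In SAP 5.4.1 and Table 4:

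1. For subjects who complete treatment, state that diary days after the Visit 8 date do not enter the Week 16 window, which then runs from Day 99 to the earlier of Day 112 and the Visit 8 date.
2. Define the end of the Double-Blind Period as the actual Visit 8 date, and use each diary day in one window only.
3. For early terminators, state whether post-termination days count in the Week 2–16 windows, and report the primary analysis with and without them.
4. Reconcile Table 4 with SAP 2.1 and Protocol 10.2, and list the change in SAP section 8.

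Truncation does not turn the window into the literal 14 days before Visit 8. With Visit 8 on Day 120 it still omits 8 on-treatment days (113–120). It does avoid the overlap with Week 14 that full re-anchoring would cause, and the reconciled text should say that this is intended.

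The cost is a few SAP sentences, one date condition in the derivation and one extra run of the primary model. Week 16 means for completers seen on Days 106–111 will rest on 8 to 13 calendar days instead of 14. In the run without post-termination days, some early terminators will have no Week 16 value, which the mixed model accommodates under missing at random.

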**Table 4 Analysis Visit Window for diary data**

Analysis Visit	Nominal day	Window
Baseline	-1	Day -14 to -1
Week 2	14	Day 1 to 14
Week 4	28	Day 15 to 28
Week 6	42	Day 29 to 42
Week 8	56	Day 43 to 56
Week 10	70	Day 57 to 70
Week 12	84	Day 71 to 84
Week 14	98	Day 85 to 98
Week 16	112	Day 99 to 112
Week 22 (FU)		the latest 1 to 14 days before FU not overlapping with the Double-Blind Period.

#### 5.4.1.1 The average daily time to first prodromal symptom associated with exposure to sunlight

The following is the procedure to calculate the average daily time to first prodromal symptom associated with exposure to sunlight.

1. If the sunlight exposure time is beyond the interval (from 1 hour post sunrise to 1 hour pre-sunset), then this time is excluded by comparing the sunrise/sunset time.
2. The time to first prodromal symptom associated with exposure to sunlight in a day is calculated. It is the sum of the sunlight exposure time before the first prodromal symptom occurred in the day. If a subject had sunlight exposure but no prodromal

symptom in a day, the sum of the sunlight exposure time for the day is used as the sunlight exposure time to the first prodromal symptom.

3. A diary day is qualified if the subject had non-zero duration of sunlight exposure in the day.
4. The average daily sunlight exposure time to the first prodromal symptom at a time point (Baseline, Week 2, 4, 6, 8, 10, 12, 14, 16, and 22) is the average of the sunlight exposure time to the first prodromal symptom of qualified days in the corresponding 14-day window. At least 1 day diary data is required for each 14 day window to be qualified for this calculation.
5. The minute is used as the unit for calculation of the duration. The Duration will not be rounded. However, in data presentation for listings, the duration will be rounded to integer. HH:MM can be used when the duration is more than 60 minutes. For tables, the duration will be rounded to integer for minimum and maximum and to one decimal place for mean, SD, median and confidence intervals.

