2.2 Study Endpoints

2.2.1 Primary Efficacy Endpoint

- Change from baseline in average daily time (minutes) to first prodromal symptom associated with sunlight exposure between 1 hour post sunrise and 1 hour pre-sunset at Week 16 (Visit 8).

To calculate the average daily duration, a 14-day window on or before a visit/time-point (Week 2, 4, 6, 8, 10, 12, 14, and 16) will be used. For baseline, a 14-day window before Day one will be used. A 14-day window will be applied to similar situations for other efficacy endpoints.

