4.7.2 Physical Activity and Subject Sun Exposure

Subjects will be encouraged to go outside during daylight hours (e.g., between 1 hour post sunrise and 1 hour pre-sunset) during the treatment period by the investigators or designated study site staff. Time outside should be correlated with or limited by the onset of prodromal symptoms. Subjects will be asked to make note of time period spent outside or until the onset of prodromal symptoms in the sunlight exposure diary. Outside exposure is considered locations outside of a building such as the time riding in a car or train. Time next to a window indoors is not considered outside exposure.

Patients will be informed by the investigator regarding the objectives of the study and the importance of the patient seeking some level of direct sun exposure on a daily basis. This discussion will include clarification that the goal is not to intentionally induce phototoxic reactions, but for the subject to spend enough time to generate some level of prodromal symptoms. The goal of the study is to determine whether the study drug has an effect on increasing the symptom-free time in the sun and/or reducing the duration or intensity of symptoms associated with sun exposure. Once randomized, no subject will be coerced into direct sun exposure that would induce phototoxicity, or discontinued for noncompliance if the subject expresses a concern for their own safety and well-being.

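### As written, the primary-endpoint derivation lets a symptom from excluded pre-window exposure stop the clock, so a day with a symptom-free eligible outing can score 0

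*SAP*

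**What the plan says.** The primary endpoint is the change in daily time to the "first prodromal symptom associated with sunlight exposure between 1 hour post sunrise and 1 hour pre-sunset at Week 16" (Protocol 2.2.1; SAP 2.1 agrees). The event is thus tied to exposure inside the interval.

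SAP 5.4.1.1 turns this into steps:

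- Step 1 deals with exposure time beyond the interval: "then this time is excluded by comparing the sunrise/sunset time". It does not mention symptom records.
- Step 2 gives the daily score: "It is the sum of the sunlight exposure time before the first prodromal symptom occurred in the day". If there was exposure but no symptom, the whole day's exposure is used.
- Step 3 decides which days count: "A diary day is qualified if the subject had non-zero duration of sunlight exposure in the day". It does not say whether this is judged before or after trimming.
- Step 4 averages the qualified days in each 14-day window: "At least 1 day diary data is required for each 14 day window to be qualified for this calculation".

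The eDiary and missing-data rules (SAP 7.15.2 and 7.15.3) do not drop or reassign a symptom whose exposure was trimmed away.

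**The concern.** Steps 1 and 2 treat the two halves of one diary episode differently: the exposure goes and the symptom it produced stays. A symptom before the window opens precedes every eligible minute of the day, so nothing is left to sum. If the subject later goes out inside the interval without symptoms, the day qualifies and enters the average as 0.

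Such records can occur. Protocol 4.7.2 counts travel: "Outside exposure is considered locations outside of a building such as the time riding in a car or train". Complete, correct diary entries are enough to trigger the rule.

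At stake is the primary variable itself. The derivation feeds the post-baseline responses and the baseline covariate in the MMRM (SAP 7.11.1). With 34 subjects per group and no formal sample-size calculation (SAP 6), avoidable noise here is unwelcome.

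**Working it through.** The plan gives no figure to reproduce, so the check applies the steps to illustrative diary days.

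**Inputs.** The clock times are the SAP's fallback sunrise and sunset of 6:00 and 18:00 (SAP 7.15.1), so the interval is 07:00–17:00. The diary days and the intended daily values are assumptions.

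**Formula.** After trimming each exposure to the interval, the daily score is the sum over exposures of max(0, min(trimmed end, onset) − trimmed start). Without a symptom it is the sum of trimmed durations.

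**Main case (day A).** Exposure 6:30–6:50 with onset at 6:45, then symptom-free exposure 12:00–13:00.

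- The first exposure is trimmed to nothing.
- For the second, min(13:00, 6:45) − 12:00 is negative, so it contributes 0. Score: **0**.
- If the excluded exposure's symptom does not stop the clock: 13:00 − 12:00 = **60 minutes**.
- SAP 5.4.1.2 (first secondary endpoint) uses the same trim but deducts only symptom time overlapping an exposure period. If the early symptom has resolved by noon, it gives **60 minutes** for the same day.

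**Other cases, in minutes.** The last column is the rule proposed below.

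| Day | Diary record | As written | Untrimmed time before onset | Proposed primary rule |
|---|---|---|---|---|
| A | 6:30–6:50, onset 6:45; 12:00–13:00 symptom-free | 0 | 15 | 60 |
| B | 6:30–7:30, onset 7:20 | 20 | 50 | 20 |
| D | 12:00–13:00 symptom-free; 17:10–17:40, onset 17:30 | 60 | 80 | 60 |
| E | 6:30–7:30, onset 6:50 | 0 | 20 | 0 |
| F | 6:30–6:50, onset 6:45; nothing else | 0, or not qualified | 15 | not qualified |

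Day D shows that the fault is one-sided: a symptom wholly after the window takes away no eligible minutes already accrued. Days B and E straddle the opening; their exposure does contribute in-window minutes, so they are a different matter. Day F shows the gap in step 3: the day enters as 0 if qualification uses untrimmed exposure and drops out if it uses trimmed exposure.

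**Effect on a 14-day average.** With q qualified days, k of them wrongly zero, and an intended value T on every day, the mean falls from T to T(q − k)/q, a loss of T·k/q. For T = 60 and k = 1:

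- q = 14: 60/14 = 4.3 minutes
- q = 10: 60/10 = 6 minutes
- q = 7: 60/7 = 8.6 minutes
- q = 3: 60/3 = 20 minutes
- q = 1, which step 4 allows: 60 minutes, so the window value is 0

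For T from 30 to 120 with q = 14, one such day costs 30/14 = 2.1 to 120/14 = 8.6 minutes.

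**The case against.** The best defence is that the text can be read the intended way. The opening of step 2 describes the event as associated with sunlight exposure, and SAP 5.4.1 begins with a general convention, "For this study, only the sunlight exposure between 1 hour post sunrise and 1 hour pre-sunset is considered and collected", adding that this wording will not be repeated. Together these could mean that a symptom from wholly excluded exposure never counts, and day A would score 60. No sentence says outright that such a symptom is kept.

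That reading is possible, but it does not override the formula in step 2, which refers to the day without qualification. Nor can the convention be literally true of collection: SAP 5.4.1 goes on to exclude out-of-window time at analysis, and 5.4.1.2.1 derives an endpoint regardless of time of day, which needs those records. At best, two programmers could score the same day 0 and 60.

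Other points against a larger claim do stand. The blinded data review may add handling rules (SAP 7.1), further diary detail sits in a reference manual not among the documents, and the first secondary endpoint avoids the zero once the symptom has resolved.

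A reader might also infer more than the documents support:

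- *That the shortened time on straddling days is the same fault.* It largely follows from counting only in-window minutes. On day B the symptom lies inside the window and belongs to an eligible exposure.
- *That seasonal movement of the window or winter commuting makes this common.* No figure supports either. Counting travel as exposure shows only that such records can arise.
- *That the most sensitive subjects lose most.* By T·k/q, one zero day costs more minutes when T is larger. Only a higher frequency in sensitive subjects could reverse this, and no frequency is given.

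**Conclusion.** The concern holds for symptoms arising wholly from exposure before the window. The literal rule gives a primary value at odds with the endpoint definition: 0 instead of 60 minutes in the worked case, and a window mean lower by 4.3, 6 or 8.6 minutes for one such day among 14, 10 or 7 qualified days. These sizes assume an intended 60 minutes on every day and a 07:00 opening.

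A reader might conclude that the treatment comparison is biased. The documents do not show that. The rule is the same in every arm and its frequency is unknown, so what is certain is distortion and added noise in baseline and follow-up values where it applies. A difference between arms would require treatment to change when subjects go out or whether they have early symptoms. That is possible but cannot be sized here. The point should be settled before unblinding.

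**What to change.** In SAP 5.4.1.1:

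1. **Step 2.** Stop the clock only at a symptom whose linked exposure record contributes minutes inside the interval. Ignore symptoms linked only to excluded exposure, but credit no eligible minutes while such a symptom is still present by its recorded recovery time. On day A with recovery at 12:20, the score would be 13:00 − 12:20 = 40 minutes.
2. **Step 3.** State that qualification uses trimmed exposure, so day F is not counted.
3. **Straddling exposures.** Keep the in-window count in the primary analysis (days B and E stay at 20 and 0). Add one sensitivity MMRM that uses untrimmed minutes for those episodes (50 and 20). Do not drop these days because a symptom occurred, since that would select on the outcome.

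The data allow this: subjects record symptom onset and recovery for each exposure (Protocol 6.7.1.1), and SAP 7.15.3 already relies on a link from symptom to exposure record. The sentence in SAP 5.4.1 about what is collected should be reconciled with 5.4.1.2.1 at the same time.

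The cost is a few sentences, one filter in the derivation program and one extra model run.
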